3.5. Safety Endpoints

- *Adverse Events;*
- *Standard safety assessments (safety laboratory testing [chemistry, hematology], sitting vital signs, electrocardiogram (ECG [12-lead]));*
- *Joint safety adjudication outcomes;*
- *Total joint replacements;*
- *Neurologic examination (Neuropathy Impairment Score [NIS]);*
- *Orthostatic (supine/standing) blood pressure assessments;*
- *Survey of Autonomic Symptom scores;*
- *Anti-drug antibody (ADA) assessments;*
- *Physical examinations.*

3.5.1. Adverse Events

An adverse event is considered treatment emergent relative to a given treatment if:

- the event occurs for the first time during the effective duration of treatment and was not seen prior to the start of treatment (for example, during the baseline or run-in period), or
- the event was seen prior to the start of treatment but increased in severity during treatment.

The effective duration of treatment is determined by the lag time. Any event occurring within the lag time, whether this occurs during a break in treatment or at the end of treatment, is attributed to the corresponding treatment period. An infinite lag will be used for the study, meaning any treatment-emergent AE reported in the database will be included in tables of AEs up to end of study.

The adverse events of Abnormal Peripheral Sensation (APS) are defined in the table below.

Allodynia	Neuritis
Axonal neuropathy	Neuropathy peripheral
Burning sensation	Paraesthesia
Carpal Tunnel Syndrome	Paraesthesia oral
Decreased Vibratory Sense	Peripheral sensorimotor neuropathy
Demyelinating polyneuropathy	Peripheral sensory neuropathy
Dysaesthesia	Polyneuropathy
Formication	Polyneuropathy chronic
Hyperaesthesia	Sensory disturbance
Hyperpathia	Sensory loss
Hypoaesthesia	Thermohypoaesthesia
Hypoaesthesia oral	Sciatica
Intercostal neuralgia	Tarsal Tunnel Syndrome
Neuralgia	

Adverse Events of Sympathetic Nervous System are defined in the table below.

Abdominal discomfort	Micturition urgency
Anal incontinence	Nausea
Anhidrosis	Nocturia
Blood pressure orthostatic decreased	Orthostatic hypotension
Bradycardia	Pollakiuria
Diarrhoea	Presyncope
Dizziness postural	Respiratory distress
Early satiety	Respiratory failure
Ejaculation delayed	Sinus bradycardia
Ejaculation disorder	Syncope
Ejaculation failure	Urinary hesitation
Heart rate decreased	Urinary incontinence
Hypertonic bladder	Vomiting
Hypohidrosis	

A smaller set of the above Adverse Events (to be called AEs of Decreased Sympathetic Function) may also be summarized. These are defined below.

Anhidrosis	Orthostatic hypotension
Bradycardia	Syncope
Hypohidrosis	

The lists given above may be updated depending on any additional adverse events observed in any tanezumab study. There are a number of summaries based on these groupings of adverse events.

A 3-tier approach will be used to summarize AEs. Under this approach, AEs are classified into 1 of 3 tiers. Different analyses will be performed for different tiers. A description of the three tiers and analyses are given in [Section 6.6.1](#).

All summaries of adverse events will be shown for adverse events that begin or worsen from the first SC dose (treatment-emergent) up to the end of the treatment period. In addition a selection of adverse event tables will be produced for the safety follow-up period and for the whole period up to the end of the study, including the treatment period and safety follow-up period.

3.5.2. Vital Signs

The incidence of orthostatic hypotension at each visit, at any treatment period visit (including unscheduled visits), and at any safety follow-up period visit (including unscheduled visits), will be summarized. The definition of orthostatic hypotension is:

- For patients with Baseline supine systolic Blood Pressure ≤ 150 mmHg:
 - Reduction in sBP (standing minus supine) ≥ 20 ; OR
 - Reduction in dBP (standing minus supine) ≥ 10 .
- For patients with Baseline supine systolic Blood Pressure > 150 mmHg:
 - Reduction in sBP (standing minus supine) ≥ 30 ; OR
 - Reduction in dBP (standing minus supine) ≥ 15 .

An additional summary will be provided of outcomes of assessments resulting from an incident of orthostatic hypotension or other events of interest, using data from both the CRF database and the consultation database, as appropriate.

3.5.3. Total Joint Replacement and Surgical Endpoints

A summary of adjudication outcomes (including outcomes of rapidly progressive osteoarthritis (type-1 only), rapidly progressive osteoarthritis (type-2 only), rapidly progressive osteoarthritis (type-1 or type-2 combined), subchondral insufficiency fracture,

primary osteonecrosis, and pathological fracture) and total joint replacements will be provided.

Reporting of total joint replacement events including surgery and recovery will be described in a separate Statistical Analysis Plan for Study 1064, and reported in the 1064 study report. Corresponding data from Studies 1056, 1057 and 1058 will be reported under study 1064, as well as patients who enter study 1064 from studies 1059, 1061, and 1063 due to those studies closing out.

3.5.4. Neurological Endpoints

The Neuropathy Impairment Score (NIS) is the sum of scores over all 37 items from both the Left and Right side. Items 1-24 are scored on a 0-4 scale (0, 1, 2, 3, 3.25, 3.5, 3.75, 4) and items 25-37 are scored on a 0-2 scale (0, 1, 2). The possible range of the NIS is 0-244.

The Survey of Autonomic Symptoms (SAS) is a 12 item (11 for females) questionnaire. From this the total number of symptoms (0-12 for males and 0-11 for females) will be calculated. Where a patient has a symptom, the impact of that symptom is then rated from 1 ('not at all') to 5 ('a lot'). The total impact score is calculated using this 1-5 scale, with 0 assigned where the patient does not have the particular symptom. The range for the total impact score is 0-60 for males and 0-55 for females.

4. ANALYSIS SETS

Data for all subjects will be assessed to determine if subjects meet the criteria for inclusion in each analysis population prior to unblinding and releasing the database and classifications will be documented per standard operating procedures.

If a subject was:

- Randomized but not treated, then that subject will be excluded from all efficacy and safety analyses.
- Treated but not randomized, then by definition that subject will be excluded from the efficacy analyses, but will be reported under the treatment they actually received for all safety analyses.
- Randomized but received incorrect treatment, then that subject will be reported under their randomized treatment group for all efficacy analyses, but will be evaluated on a case-by-case basis for presentation for safety analyses. Decisions will be made before unblinding.

4.1. Full Analysis Set

The intent to treat (ITT) analysis set is the primary analysis set for efficacy analyses. It consists of all randomized subjects who received at least one dose of SC study medication (either tanezumab or placebo SC). This analysis set is used in the presentations of all

efficacy data, and all data listings, and is labeled as the ‘ITT Analysis Set’ or ‘ITT Population’.

4.2. Per Protocol Analysis Set

The per-protocol (PP) analysis set is the secondary efficacy analysis set. It is defined as all subjects in the ITT analysis set who are not major protocol deviators (which would potentially affect efficacy). The criteria for major protocol deviators are described below in [Sections 4.2.1](#) and [4.2.2](#). The identification of specific subjects included and excluded (and reason for exclusion) for this analysis set will be made and documented prior to unblinding. Protocol deviations for the PP analysis set will be obtained from the collected list of potentially important protocol deviations, and this list will comprise deviations identified from review of programmed listings and study monitoring. This analysis set is used in a specific sensitivity analysis of the co-primary efficacy endpoints, and is labeled as the ‘Per Protocol Population’.

Any other major deviation which is not pre-specified below, but results in a subject being excluded from the PP analysis set, will be specified in the protocol deviations document which is completed prior to unblinding.

The following protocol deviations are defined as ‘major’ and would exclude a subject from the PP analysis set. These deviation criteria can be split into those assessed prior to randomization relating to the protocol inclusion and exclusion criteria, and those assessed post randomization.

4.2.1. Major Deviations Assessed Prior to Randomization

- Inclusion criteria: #3-5.
- Exclusion criteria: #3, 4 (if any of the following conditions are in the index joint: severe chondrocalcinosis, other arthropathies [eg, rheumatoid arthritis], systemic metabolic bone disease [eg, pseudogout, Paget’s disease, metastatic calcifications], primary or metastatic tumor lesions, stress or traumatic fracture), 10, 14, 15, 16 (if index joint was involved), 17.
- Randomization criteria: #1, 3-6. Note, subjects with missing Baseline data for any of the co-primary endpoints would not meet the randomization/inclusion criteria for Baseline co-primary endpoints and so would be defined as a deviation according to these criteria.

4.2.2. Major Deviations Assessed Post-Randomization

- Mismatch in specification of index joint in the CRF vs. electronic tablet for WOMAC data collection.
- Rescue medication taken within 24 hours prior to the Week 16 visit

- Prohibited medications that could affect pain and function assessments (protocol section 5.8.1) taken (i) within 48 hours prior to Week 16 visit for non-NSAID medications (or any use if long-acting, eg, Synvisc), or (ii) within 48 hours prior to Week 16 visit or within the wash-out period specified by Appendix 3 of the protocol, for NSAID medications.

In addition, unforeseen major protocol deviations may be added to this list. However the final definition of this criteria and the per-protocol population will be made prior to unblinding of this study.

4.3. Safety Analysis Set

The safety analysis set is defined as all subjects treated with tanezumab or placebo SC (see beginning of Section 4 for further details). This analysis set will be labeled as the ‘Safety Analysis Set’ or ‘Safety Population’ in the corresponding data analyses and summary presentations.

4.4. Other Analysis Sets

Not applicable.

5. GENERAL METHODOLOGY AND CONVENTIONS

5.1. Hypotheses and Decision Rules

5.1.1. Statistical Hypotheses

The treatment comparisons being made in this study are tanezumab 2.5 mg and 2.5 mg then 5 mg (2.5/5 mg) versus placebo. For these treatment comparisons, the null and alternative hypotheses are shown below (note $\mu_{\text{TREATMENT}}$ relates to the mean change from Baseline for the specified treatment group). All tests will be 2-sided.

Null Hypotheses	H0: $\mu_{\text{TANEZUMAB 2.5mg}} - \mu_{\text{PLACEBO}} = 0$
	H0: $\mu_{\text{TANEZUMAB 2.5/5mg}} - \mu_{\text{PLACEBO}} = 0$
Alternative Hypotheses	H1: $\mu_{\text{TANEZUMAB 2.5mg}} - \mu_{\text{PLACEBO}} \neq 0$
	H1: $\mu_{\text{TANEZUMAB 2.5/5mg}} - \mu_{\text{PLACEBO}} \neq 0$

The hypotheses for other types of analyses (e.g. for the binary response endpoints) would be similar to those shown above.

5.1.2. Statistical Decision Rules

The Type I error rate (α -level) used in the assessment of pair-wise treatment comparisons for the primary efficacy endpoints is 5%. The fixed sequence testing strategy of the co-primary endpoints is described below.

The assessment of significance for the tanezumab versus placebo treatment contrasts will use a step-down testing strategy within each of the co-primary efficacy endpoints. The step-down testing will first test tanezumab 2.5/5 mg versus placebo, and if statistically significant ($p \leq 0.05$) will then test tanezumab 2.5 mg versus placebo. Finally, the particular tanezumab dose group is declared as superior to placebo if the corresponding treatment contrast is significant over all three co-primary endpoints. This testing procedure will maintain the Type I error to 5% or less within each of the co-primary efficacy endpoints, and to less than 5% for all three co-primary efficacy endpoints.

The secondary endpoint of subjects with $\geq 50\%$ reduction from baseline in WOMAC Pain at Week 16 is identified as a key secondary endpoint and will be included in the testing strategy. If both tanezumab regimens are found to be statistically significantly better than placebo in the primary comparisons described above, the two comparisons of this secondary endpoint (tanezumab 2.5 mg treatment group versus placebo and tanezumab 2.5/5 mg treatment group versus placebo) will be adjusted for multiple comparisons using the Hochberg procedure and an overall significance level of 0.05.

The primary analysis will be that with the multiple imputation approach (see below for details), and thus the overall type I error is controlled for each of the two dose regimens (2.5 mg and 2.5/5 mg) since all three co-primary endpoints need to be significant for a single dose. The overall type I error of the study is also controlled given the step-down testing strategy for each of the primary endpoints and the key secondary endpoint. Control of the type I error rate accounting for multiplicity of contrasts will only apply to the three co-primary endpoints (model with the primary imputation analysis) and the key secondary endpoint.

Regardless of the outcome of the primary and key secondary analyses, the secondary endpoints will be tested. No adjustment for multiple comparisons will be made for the secondary efficacy, and for the safety endpoints. The α -level for each hypothesis test for the secondary and exploratory analyses will be 5%.

5.2. General Methods

Subjects will be randomized at Baseline to one of three treatment groups: placebo SC, tanezumab 2.5 mg SC, or tanezumab 2.5/5 mg SC. These will be labeled as placebo, tanezumab 2.5 mg, and tanezumab 2.5/5 mg for the three treatment groups respectively.

A modified treatment-policy estimands strategy is applied as the main strategy to assess effectiveness of tanezumab. Data collected will be included for efficacy assessment regardless of rescue medication being used or not.

The general study design for efficacy, as depicted below, includes a planned treatment period through the Week 16 visit, and a planned 24-week post-treatment safety follow-up period. Efficacy data planned to be collected during this post-treatment safety follow-up period are intended to have efficacy measures contemporaneous to safety observations during this period. They are not intended to assess treatment effects or compare treatment groups. *All*

endpoints up to Week 24 will be summarized (where available), and endpoints up to Week 16 will be analyzed.

1056 Study Visits / Analysis Windows

Week	B	2	4	8	12	16	24			40
Day	1	15	29	57	85	113	169			281
completer	x	x	x	x	x	x	x			
drop after Day 1 dose	x	x	x	x ET1		x ET2				

B = Baseline; x = collection of most efficacy endpoints; ET = Early Termination Visit

The method and definition of reporting windows for assigning efficacy data to particular time points is described in Appendix 2.1.

All efficacy assessments during the treatment period are made on the analysis windows defined in Appendix 2.1. Using these windows we find the analysis window for a subject’s last subcutaneous (SC) dose. Any data included in a window that is up to 8 weeks from this last SC dose window is ‘on-treatment’, and any data included in a window that is more than 8 weeks after the last SC dose window is off-treatment. Data in on-treatment analysis windows will be used in summaries and analyses, while data in off-treatment analysis windows will be excluded from all summaries and analyses of treatment period efficacy data, ie, up to Week 16.

For example, the table below shows on-treatment and off-treatment windows for the planned collection visits for the WOMAC data during the treatment period:

Last SC Dose Analysis Window	On-treatment Analysis Window Data	Off-treatment Analysis Window Data
Baseline	Weeks 2, 4, 8	Weeks 12, 16
Week 2	Weeks 2, 4, 8	Weeks 12, 16
Week 4	Weeks 2, 4, 8, 12	Week 16
Week 8	Weeks 2, 4, 8, 12, 16	None
Week 12	Weeks 2, 4, 8, 12, 16	None
Week 16	Weeks 2, 4, 8, 12, 16	None

Efficacy data at Week 24 is planned to be off-treatment so will not be subject to the above handling, ie, all available data in the Week 24 window will be used in summaries.

Efficacy data collected via subject diary (NRS pain scores and rescue medication use) are collected daily or weekly, not at study visits. Diary efficacy data will be considered on-treatment if it is collected up to 12 weeks (84 days) after the last SC dose. Diary efficacy data collected more than 12 weeks (84 days) after the last SC dose will be considered off-

treatment and excluded from summaries and analyses of treatment period efficacy data, ie, for presentations up to Week 16.

Diary data after Week 16 is planned to be off-treatment so will not be subject to the above handling, ie, all available data in windows after Week 16 will be used in summaries.

A summary of all analyses is given in Appendix 1. In all tables the treatment group ordering will be: placebo, tanezumab 2.5 mg, tanezumab 2.5/5 mg. Unless otherwise specified, efficacy analyses use the ITT analysis set only.

5.2.1. Analyses for Binary Data

Binary response parameters, and the incidence of rescue medication use and treatment discontinuation due to lack of efficacy will be analyzed using logistic regression for binary data, with covariates described in [Section 3.4.1](#). Output will show the number and percentage of subjects in each response category, and odds ratios (with 95% confidence intervals) for the treatment comparisons shown in [Section 5.1.1](#).

Subject response endpoints of the OMERACT-OARSI responder criteria, improvement in the WOMAC Pain ≥ 30 , 50, 70 and 90%, WOMAC Physical Function ≥ 30 , 50, 70 and 90%, and improvement in the Patient's Global Assessment of Osteoarthritis ≥ 2 will be analyzed for change from Baseline to Weeks 2, 4, 8, 12 and 16, using logistic regression for binary data, with model terms for baseline WOMAC Pain subscale score, WOMAC Physical Function subscale score, or Patient's Global Assessment score (Baseline WOMAC Pain for OMERACT-OARSI responder index), Baseline diary average pain, index joint, Kellgren-Lawrence grade, and treatment group. Imputation for missing data will use both LOCF and BOCF, where imputation with BOCF will lead to the subject being assessed as a non-responder for the response endpoint at a particular timepoint. In addition, in order to closely match the primary imputation analysis, a mixed BOCF/LOCF imputation for response endpoints will be used. In this analysis BOCF imputation (ie, a subject would be a non-responder) would be used for missing data due to discontinuation for reasons of lack of efficacy ('Insufficient Clinical Response' on the End of Treatment Subject Summary Case Report form), adverse event or death up to the timepoint of interest, and LOCF imputation would be used for missing data for any other reason.

The use of BOCF for missing data implies subjects with missing data are included in the analysis as non-responders. Similarly the use of LOCF in the case where subjects have no post-Baseline data (and Baseline would be carried forward) again implies those subjects are included in the analysis as non-responders.

The incidence ... of use of rescue medication... will be analyzed for Weeks 2, 4, 8, 12, and 16... The incidence of use of rescue medication will be analyzed using logistic regression for binary data, with model terms for Baseline WOMAC Pain subscale score, Baseline diary average pain, index joint, Kellgren-Lawrence grade, and treatment group. ... Estimated levels of rescue medication use will be shown for each treatment group, and the ratio (with

95% CI) for comparisons versus placebo will be shown. Imputation for missing rescue medication data will use LOCF only.

The incidence of treatment withdrawal due to lack of efficacy ('Insufficient Clinical Response' on the Subject Summary Case Report form) will also be analyzed for discontinuation up to Week 16 (end of treatment period). The analysis of the incidence of discontinuation due to lack of efficacy will be made using logistic regression for binary data, with model terms for Baseline WOMAC Pain subscale score, Baseline diary average pain score, index joint, Kellgren-Lawrence grade, and treatment group. Discontinuation in the post-treatment safety follow-up period will not be included in this endpoint for analysis, but will be summarized as part of the safety tables.

Cumulative WOMAC Pain response and WOMAC Physical Function at Week 16 using response definitions from a reduction of >0% to =100% (in steps of 10%) will be summarized, using mixed BOCF/LOCF (as described above), and also LOCF and BOCF imputation for WOMAC Pain and WOMAC physical function. Imputation with BOCF for subjects with missing data at that timepoint will lead to the subjects being assessed as non-responders for the response endpoint.

The proportion of subjects who meet a WOMAC Pain response definition at Week 16 will be examined in the cohort of subjects who had a WOMAC Pain response to treatment at Week 8 and the cohort of subjects who did not have a WOMAC Pain response at Week 8. Treatment comparisons will be made within each cohort for tanezumab 2.5/5 mg versus placebo and tanezumab 2.5 mg versus placebo. A descriptive comparison will also be made between the treatment groups of tanezumab 2.5/5 mg versus tanezumab 2.5 mg. These analyses will be produced for the WOMAC Pain response levels of 30% and 50%, and other response definitions (15%). This is an exploratory analysis as treatment comparisons are not specifically powered to achieve significance within cohorts of subjects.

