2.1.2. Secondary Objectives

[figure not shown]
Evaluate treatment benefit (efficacy) of a tanezumab 2.5 mg SC titration to 5 mg SC dosing regimen relative to tanezumab 2.5 mg SC alone (descriptive analyses);

Evaluate the safety of tanezumab 2.5 mg SC and tanezumab 2.5 mg SC titration to 5 mg SC regimens.

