Percentage of subjects with reduction of $\geq 30/50/70/90\%$ from Baseline to Weeks 2, 4, 8, 12, and 16 in the WOMAC Physical Function subscale	ITT	Logistic Regression	BL Score, BL diary average pain, Index Joint (Knee/Hip), Highest KL grade (2, 3 or 4), Treatment Group	LOCF	Secondary Endpoint Analysis
Percentage of subjects with an improvement of ≥ 2 points from Baseline to Weeks 2, 4, 8, 12, and 16 in the Patient Global Assessment of Osteoarthritis	ITT	Logistic Regression	BL Score, BL diary average pain, Index Joint (Knee/Hip), Highest KL grade (2, 3 or 4), Treatment Group	Mixed BOCF/LOCF	Secondary Endpoint Analysis
Percentage of subjects with an improvement of ≥ 2 points from Baseline to Weeks 2, 4, 8, 12, and 16 in the Patient Global Assessment of Osteoarthritis	ITT	Logistic Regression	BL Score, BL diary average pain, Index Joint (Knee/Hip), Highest KL grade (2, 3 or 4), Treatment Group	BOCF	Secondary Endpoint Analysis
Percentage of subjects with an improvement of ≥ 2 points from Baseline to Weeks 2, 4, 8, 12, and 16 in the Patient Global Assessment of Osteoarthritis	ITT	Logistic Regression	BL Score, BL diary average pain, Index Joint (Knee/Hip), Highest KL grade (2, 3 or 4), Treatment Group	LOCF	Secondary Endpoint Analysis
Percentage of subjects with reduction of $\geq 30/50\%$ from Baseline to Week 16 in the WOMAC Pain subscale, separately for Week 8 Responders and Non-Responders (same definition as Week 16)	ITT	Logistic Regression	BL Score, BL diary average pain, Index Joint (Knee/Hip), Highest KL grade (2, 3 or 4), Treatment Group	Mixed BOCF/LOCF	Exploratory Analysis
Reduction of $>0\%$, $\geq 10\%$, to $\geq 90\%$ (in steps of 10%) and $=100\%$ from Baseline to Week 16 in the WOMAC Pain subscale	ITT	None (summary and plot)	NA	Mixed BOCF/LOCF	Summary of secondary endpoint
Reduction of $>0\%$, $\geq 10\%$, to $\geq 90\%$ (in steps of 10%) and $=100\%$ from Baseline to Week 16 in the WOMAC Pain subscale	ITT	None (summary)	NA	BOCF	Summary of secondary endpoint

Reduction of >0%, ≥10%, to ≥90% (in steps of 10%) and =100% from Baseline to Week 16 in the WOMAC Pain subscale	ITT	None (summary)	NA	LOCF	Summary of secondary endpoint
Reduction of >0%, ≥10%, to ≥90% (in steps of 10%) and =100% from Baseline to Week 16 in the WOMAC Physical Function subscale	ITT	None (summary and plot)	NA	Mixed BOCF/LOCF	Summary of secondary endpoint

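### Tanezumab is compared with placebo within Week 8 responder and non-responder cohorts, which are not randomised comparisons, and the SAP's only caveat is low power

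*SAP*

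**What the plan says.** SAP Section 5.2.1 forms two cohorts from WOMAC Pain response at Week 8 and examines Week 16 response in each. On the contrasts it says: "Treatment comparisons will be made within each cohort for tanezumab 2.5/5 mg versus placebo and tanezumab 2.5 mg versus placebo". For the two active arms it adds: "A descriptive comparison will also be made between the treatment groups of tanezumab 2.5/5 mg versus tanezumab 2.5 mg". Its one caveat is: "This is an exploratory analysis as treatment comparisons are not specifically powered to achieve significance within cohorts of subjects".

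Appendix 1 lists the analysis as logistic regression, "separately for Week 8 Responders and Non-Responders (same definition as Week 16"), with baseline score, baseline diary pain, index joint, Kellgren-Lawrence grade and treatment as terms. Missing data are handled by mixed BOCF/LOCF, and the objective is labelled exploratory.

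Three general rules decide how the placebo contrasts will be reported:

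- Section 5.1.1 defines the comparisons: "The treatment comparisons being made in this study are tanezumab 2.5 mg and 2.5 mg then 5 mg (2.5/5 mg) versus placebo".
- Section 5.2.1 gives binary response parameters "odds ratios (with 95% confidence intervals) for the treatment comparisons shown in" Section 5.1.1.
- Section 5.1.2 says the level "for each hypothesis test for the secondary and exploratory analyses will be 5" per cent.

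**The concern.** Section 2.2 gives the arms tanezumab or placebo from Day 1, so treatment has already differed for eight weeks when the cohorts are formed. Section 5.2.1 itself analyses Week 8 response as an outcome of treatment. The cohorts are thus defined by something the drug is meant to change.

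If the drug turns some subjects into Week 8 responders, the tanezumab responders include people who would have been non-responders on placebo, and the tanezumab non-responders are what remains. The subjects compared within a cohort then differ in kind as well as in treatment. The model terms are all baseline variables, whereas the selection acts on response after dosing, so adjustment does not restore comparability.

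A reader warned only about power would take a cohort odds ratio to be imprecise but unbiased. A larger trial would narrow its interval around the same biased value.

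The labels also sit the wrong way round. The two tanezumab arms receive the same dose until Week 8, so their Week 8 cohorts are comparable by randomisation. Yet this is the contrast the SAP calls descriptive, while the placebo contrasts are its treatment comparisons.

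**Working it through.** The SAP states no SD, correlation, response rate or effect size for this analysis, so there is no figure to reproduce. All inputs below are assumed and serve only to show direction and possible size.

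**Model.** Percent improvement at Weeks 8 and 16 is bivariate normal with SD 33 at each visit and correlation 0.7 in both arms. The placebo mean is 30 at both visits, and response means improvement of at least 30%. With p8 and p16 the marginal response probabilities and p11 the probability of responding at both visits:

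- Week 16 response in Week 8 responders = p11 / p8
- Week 16 response in Week 8 non-responders = (p16 − p11) / (1 − p8)

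**Placebo.** p8 = p16 = 0.500 and p11 = 0.25 + arcsin(0.7)/(2π) = 0.373.
- Responders: 0.373/0.500 = 0.747
- Non-responders: (0.500 − 0.373)/0.500 = 0.253

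**Illustration 1: every Week 8 value shifted by 10 points, Week 16 unchanged.** For tanezumab p8 = Φ(10/33) = 0.619, p16 = 0.500 and p11 = 0.426.
- Responders: 0.426/0.619 = 0.688; OR = (0.688/0.312)/(0.747/0.253) = 0.75
- Non-responders: (0.500 − 0.426)/0.381 = 0.194; OR = (0.194/0.806)/(0.253/0.747) = 0.71
- Overall: 50% in both arms; OR 1.00

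With placebo mean 25 to 35, correlation 0.5 to 0.85 and thresholds of 15, 30 and 50%, the ORs are 0.59–0.87 in responders and 0.54–0.84 in non-responders.

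**Illustration 2: the same 10-point shift at both visits.** For tanezumab p8 = p16 = 0.619 and p11 = 0.498.
- Responders: 0.805 versus 0.747; OR 1.40
- Non-responders: 0.317 versus 0.253; OR 1.37
- Overall: (0.619/0.381)/(0.500/0.500) = 1.63

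Over the same grid the cohort ORs are 1.27–1.55.

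**Illustration 3: unequal Week 8 shift, Week 16 unchanged.** The average shift stays at 10 points, but one third of subjects receive 30 and the rest receive none.
- Shift in the third with the best Week 16 values: ORs 1.14 (responders) and 0.59 (non-responders)
- Shift in the third with the worst Week 16 values: ORs 0.48 and 1.57

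These are deliberately extreme, but they show that the direction is not fixed.

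**Check from assumed response rates.** Take Week 8 response of 35% on placebo and 50% on tanezumab, Week 16 response of 40% in both arms, and correlation 0.7. Both cohort ORs are about 0.67. With 230 per arm the responders number about 80 and 115, and the non-responders about 150 and 115. The chance of p < 0.05 is then about 25% and 24%, against a nominal 5%.

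**Active arms.** With equal Week 8 response (50% and 50%) and no Week 16 difference, both cohort ORs are 1.00.

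**The case against.** The strongest defence is that little depends on this analysis. Section 5.2.1 and Appendix 1 both call it exploratory. Section 5.1.2 confines type I error control to the co-primary and key secondary endpoints. The SAP draws no causal conclusion from the cohorts, and it is plain from their definition that they are formed after randomisation. All of that stands and keeps the point minor. It does not supply the missing statement, because the reason the SAP gives for caution is power alone.

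A reader might infer from Illustration 1 that the bias always runs against tanezumab, so that the worst outcome is a misleadingly negative result. The documents do not support that. Illustration 1 assumes a Week 8 benefit that is gone by Week 16 despite the second injection, which is a legitimate null case but not the expected result. Illustration 2 gives odds ratios above 1 with the same correlation in both arms, and Illustration 3 gives spurious odds ratios above 1 with no Week 16 effect at all. None of the illustrations models dropout. Under mixed BOCF/LOCF, Week 16 status can depend on the reason for discontinuation or on the Week 8 value, so the link between the two visits may itself differ by arm.

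It is also fair to say that 2.5/5 mg versus 2.5 mg is already planned: the secondary objective is to evaluate the titration "dosing regimen relative to tanezumab 2.5 mg SC alone (descriptive analyses"). Giving it an odds ratio and interval is mainly a change of format. Nor is that contrast perfectly clean. Appendix 2.1 sets the Week 8 window at Days 44 to 71 around Day 57, so a selected value can fall after the second dose, when the two active arms may differ.

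**Conclusion.** The concern holds as a minor one. The planned contrasts with placebo within Week 8 cohorts are not randomised comparisons, baseline adjustment does not repair them, and the power-only caveat misdescribes the limitation.

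The cleanest indication of size is the null case, where an unbiased cohort odds ratio would be 1.00 and the example gives 0.75 and 0.71. With a real 10-point effect at both visits the example gives 1.40 and 1.37 against 1.63 overall. These figures rest on an assumed normal model, SD, correlation and shift. They establish that the distortion can be material, but not how large it will be in this trial or which way it will go.

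The primary and key secondary conclusions do not use these cohorts and are unaffected.

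**What to change.** In Section 5.2.1 and the matching Appendix 1 row:

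1. Within each cohort, show the placebo percentages without an odds ratio or p-value.
2. Report 2.5/5 mg versus 2.5 mg within each cohort as an exploratory odds ratio with 95% CI and no formal test. This stays within the descriptive objective of Section 2.1.2.
3. Replace the power-only caveat with a statement that the cohorts are defined after randomisation by a response that treatment can change, so contrasts with placebo within them are not randomised comparisons.
4. Keep the Week 8 window and imputation rules, so that cohort status matches the Week 8 responder endpoint. Flag and list subjects whose selected Week 8 value falls after the second dose.

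The cost is SAP wording, a changed contrast in the same model, and a simple comparison of assessment date with dose date for the flag. No new data are needed. What is lost is the exploratory placebo odds ratios within cohorts. If the sponsor prefers to keep them, the limitation statement in item 3 is the minimum.
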